3.3 Other Efficacy Endpoints

3.4 Safety Endpoints

The safety endpoints will include adverse events (AE), serious adverse events (SAE), discontinuation due to AE and the S-STS.

4 SAMPLE SIZE

The planned sample size is a total of 204 randomized subjects. This will provide approximately 80% power to detect a difference in means of 0.73 assuming that the common standard deviation is 1.7 (and accounting for 15% drop-out rate), using two-sided statistical testing with an overall Type I error rate of 0.05.

5 RANDOMIZATION

Pain scores reported by subjects during the Screening Period will be evaluated by the Interactive response technology (IRT) system for raw score and for variability among scores after transmission of pain scores from the handheld devices to determine randomization eligibility. Subjects whose mean of the daily average pain intensity score during the preceding seven (7) days is within the protocol-defined algorithm and whose compliance with daily diary completion is adequate will be eligible for randomization. The absolute pain scores and variability among scores, as well as the actual percentage required for diary compliance, will be masked to investigators and subjects. Subject eligibility for randomization into the study based on these variables will be communicated to the investigator via the IRT system. The IRT system will notify the site if the subject is "Eligible" or "Not eligible." No other information will be provided.

Eligible subjects will be randomized to receive either NYX-2925 50 mg or placebo daily in a 1:1 allocation.

6 PLANNED ANALYSES

The final Clinical Study Report (CSR) may contain additional tables or statistical tests if warranted by the data obtained. The justification for any such additional analyses will be fully documented in the final CSR.

6.1 Analysis Populations

Subjects excluded from the analysis populations and the reason for their exclusion will be listed in Appendix 16.2 of the CSR.

6.1.1 Screened Population

The Screened Population includes all subjects who are screened.

6.1.2 Randomized Population

The Randomized Population includes all subjects who were assigned a randomization number in IRT.

6.1.3 Safety Population

The Safety Population includes all subjects who received at least one dose of study drug. For safety analyses, subjects will be grouped based upon the treatment received. In the event that a subject receives both treatments (NYX-2925 and placebo), the subject will be grouped under NYX-2925.

6.1.4 Modified Intent-to-Treat Population

The Modified Intent-to-Treat (mITT) Population includes all subjects in the Safety Population with at least one post-baseline assessment of the pain intensity NRS. Efficacy analyses for the mITT Population will have subjects grouped based on their planned treatment. All efficacy analyses will be performed on the mITT Population.

6.2 Derived Data

This section describes the derivations required for statistical analysis. Unless otherwise stated, variables derived in the source data will not be re-calculated.

6.2.1 Race

Where more than one race category has been selected for a subject, these race categories will be combined into a single category labeled "Multiple" in the summary tables. The listings will reflect the original selected categories.

6.2.2 Baseline

Baseline is defined as the last non-missing value (either scheduled, unscheduled or repeat) before the subject receives the first dose of study drug.

For endpoints in which the weekly mean is being utilized, baseline is defined as the average of the available assessments on the last 7 days prior to the first dose of study drug (study days -7 to -1).

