Subjects whose mean of the daily average pain intensity score during the preceding seven (7) days within the protocol-defined algorithm and whose compliance with daily diary completion is found to be adequate will be eligible for randomization. The absolute pain scores and variability among scores, as well as the actual percentage required for diary compliance, will be masked to investigators and subjects. Subject eligibility for randomization into the study based on these variables will be communicated to the investigator via the IRT system. The IRT system will notify the site if the subject is "Eligible" or "Not eligible." No other information will be provided.

Eligible subjects will be randomized to receive either doses of oral NYX-2925 50 mg or placebo daily for 12 weeks. Investigators and subjects will be both blinded to treatment allocation and masked to the randomization criteria. Subjects will be dispensed a four-week supply of study drug and instructed to take one (1) capsule by mouth once daily. The first dose of study drug will be taken in the clinic during Visit 2 (Week 0). Subjects will be instructed to take study drug daily throughout the study. Acetaminophen will be dispensed/re-dispensed for use as rescue medication for DPN related pain; and instructions on not to exceed 2 g/day (one to two 500 mg tablets every 6 hours as needed up to 4 tablets total) will be reinforced.

Adverse events will be collected from the time of study drug administration through the last day of the subject's participation in the study.

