### 9.2.4. Daily Sleep Interference Scale

The DSIS was developed to quantify sleep interference due to pain. The DSIS is a single -item measure that is completed by patients once a day (upon awakening) to accurately capture variability in sleep interference due to pain on a daily basis, thus minimizing recall bias. The DSIS has an 11-point response scale that asks patients to "Select the number that best describes how much your pain has interfered with your sleep during the past 24 hours." Response options range from 0 (did not interfere with sleep) to 10 (completely interfered with sleep/unable to sleep due to pain). The DSIS is designed to be used in a patient daily diary that patients fill out upon awakening each morning [Vernon 2008].

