6.2.3 Duration / Study Day / Time

Study day will be calculated as the number of days from first dose of study drug.

- date of event date of first dose of study drug + 1, for events on or after first dose
- date of event date of first dose of study drug, for events before first dose

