6.2.17 Numerical Rating Scale

The Numerical Rating Scale (NRS) is a unidimensional, segmented numeric scale in which a respondent selects a whole number (0-10 integers) that best reflects the intensity of the pain. The

format is a horizontal bar or line that is anchored by terms describing pain levels where a score of 0 represents "no pain" and a score of 10 represents "worst pain imaginable". Subjects will report pain intensity during the past 24 hours daily at bedtime in the handheld diary.

NRS score will be obtained for:

- Average pain intensity related to DPN in the past 24 hours
- Average pain intensity upon walking in the past 24 hours
- Worst pain intensity related to DPN in the past 24 hours

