6.2.17.4 Time to First ≥30% and ≥50% Reduction

The time to first \geq 30% (and \geq 50%) reduction in NRS score relating to 'Average pain intensity related to DPN in the past 24 hours' will be identified as follows.

A moving average of the NRS average pain intensity will be calculated, that is, average NRS score for moving 7-day intervals from Day 1 to Day 7, from Day 2 to Day 8, from Day 3 to Day 9, and so on, up to the final interval of Day 78 to Day 84.

Percentage reduction from Baseline Mean NRS (as defined in Section 6.2.17.1) for each moving average interval will be calculated using the percentage change from baseline method described in Section 6.2.15.

The first moving average interval that yields a reduction from baseline of $\geq 30\%$ (and $\geq 50\%$) will be identified and the last day of this block of 7 days will be the date of first $\geq 30\%$ (and $\geq 50\%$) reduction.

Subjects who failed to achieve the target reduction (\geq 30% and \geq 50%) will be censored on the day of the last non-missing average pain intensity score, or the Week 12 visit date (whichever is later), for that subject.

Subjects who discontinued the study prior to Week 12 and who failed to achieve the target reduction ($\geq 30\%$ and $\geq 50\%$) while on the study will be censored at the time of discontinuation.

Time to the first \geq 30% (and \geq 50%) reduction (days) will subsequently be obtained as follows:

Date of first \geq 30% (and \geq 50%) reduction – date of dosing of study drug

6.2.18Daily Sleep Interference Scale

The Daily Sleep Interference Scale (DSIS) is a single-item measure with 11-point response scale (0-10; where 0 corresponds to "did not interfere with sleep" and 10 corresponds to "completely interfered with sleep/unable to sleep due to pain) that quantify sleep interference due to pain. The subjects complete this questionnaire daily upon awakening each morning.

Baseline mean score will be obtained as described in Section 6.2.2. Weekly mean DSIS data will be obtained for Week 12 data (and prior weeks) based on the subjects actual Week 12 visit date.

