If the subject's Week 12 visit date is within Day 80 to Day 88, then data on the actual Week 12 visit date up to 6 days prior to this date will be the corresponding data for Week 12 visit date. Consequently, the Week 11 data will be obtained by counting 7 days backwards from the 1st day of Week 12, Week 10 NRS scores will be obtained by counting 7 days backwards from the 1st day of Week 11, and the process continue up to Week 1. If the subject's actual Week 12 visit date is beyond Day 88, then the corresponding data from Day 82 to Day 88, inclusive, will be the Week 12 data. Similar process as described previously will be used to obtain the data for each week from Week 11 up to Week 1. Meanwhile, if the subject's actual Week 12 visit date is earlier than Day 80, then no Week 12 data will be identified.

Timing of Week 12 Visit	Reference Day (DSIS or Rescue Medication)
Day 80 to Day 88	Count backwards from day of Week 12 visit
Day 89+	Count backwards from Day 88 only
Earlier than Day 80	No Week 12 data identified

For subjects that withdraw early or have missing data such that they do not have any data that would fall into the Week 12 windowing, their last non-missing diary day will serve as the anchor, as described in Section 6.2.17.2.

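### The Days -7 to -1 baseline window suits bedtime pain scores but leaves the pre-dose Day 1 morning entry out of the DSIS baseline, and for some subjects that entry is then averaged into DSIS Week 1 (minor)

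*SAP*

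**What the plan says.** - **Baseline.** SAP 6.2.2 gives one window for all weekly-mean endpoints: the "average of the available assessments on the last 7 days prior to the first dose of study drug (study days -7 to -1". For the DSIS, SAP 6.2.18 adds nothing of its own: "Baseline mean score will be obtained as described in Section 6.2.2".
- **Timing of entries.** For the DSIS, SAP 6.2.18 states: "The subjects complete this questionnaire daily upon awakening each morning". Protocol 9.2.4 gives the question as "how much your pain has interfered with your sleep during the past 24 hours". For the NRS, SAP 6.2.17 states: "Subjects will report pain intensity during the past 24 hours daily at bedtime in the handheld diary".
- **First dose.** Protocol 6.1 and 8.1: "The first dose of study drug will be taken in the clinic during Visit 2 (Week 0"). SAP 6.2.3 adds one to the date difference "for events on or after first dose", so the dosing date is Day 1, the day before is Day -1, and there is no Day 0.
- **Post-baseline weeks.** For a Week 12 visit on Days 80 to 88, the DSIS rule in SAP 6.2.18 is "Count backwards from day of Week 12 visit", with earlier weeks taken as successive 7-day blocks back to Week 1. For later visits the anchor is Day 88. The NRS anchor in SAP 6.2.17.2 is one day earlier. Subjects without Week 12 data are counted back from their last diary day.
- **Use.** SAP 6.11.2.1 models DSIS change at Weeks 1 to 12 with baseline DSIS as a covariate. It presents LS means at each week, and the treatment difference with its p-value at Week 12.

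**The concern.** A bedtime score on Day -1 is the last one before dosing, so Days -7 to -1 is the right week for the NRS. For a scale answered on waking, the last pre-dose answer is on the morning of Day 1, and it describes the 24 hours before any drug was taken. The fixed window leaves that answer out, although the general rule in the same section takes the last value before the first dose.

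The entry may also reappear on the other side of the comparison. With no floor at first dose, the back-count can place the Day 1 morning in Week 1, where an untreated night is averaged as post-baseline data. At stake are the reported DSIS Week 1 mean change and, to a lesser degree, the completeness of a baseline that is both subtracted from the outcome and used as a covariate.

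**Working it through.** **1. The plan's own figure.** The only numeric DSIS window that the SAP states is for visits after Day 88. Counting seven days back from anchor Day 88 gives 88 - 6 = 82, so Week 12 is Days 82 to 88, as stated.

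**2. Week 1 as a function of the visit day.** Let *a* be the anchor (the Week 12 visit day, capped at 88). Eleven blocks of seven days separate Week 12 from Week 1:

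- last day of Week 1 = a - 77
- first day of Week 1 = a - 83
- because there is no Day 0, a result of 0 or below is lowered by one

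DSIS entries on Day 1 or earlier are pre-dose. For a of 84 or less, their number is 85 - a.

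| Week 12 visit | DSIS Week 1 | Pre-dose entries of 7 |
|---|---|---|
| Day 80 | Days -4 to 3 | 5 |
| Day 81 | Days -3 to 4 | 4 |
| Day 82 | Days -2 to 5 | 3 |
| Day 83 | Days -1 to 6 | 2 |
| Day 84 (nominal) | Days 1 to 7 | 1 |
| Day 85 | Days 2 to 8 | 0 |
| Day 86 | Days 3 to 9 | 0 |
| Day 87 | Days 4 to 10 | 0 |
| Day 88 or later | Days 5 to 11 | 0 |

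Day 1 is in Week 1 for 5 of the 9 visit days in the window. From Day 85 on it is in neither baseline nor any week. For Days 80 to 83, read literally, Week 1 also takes in mornings that are already in baseline.

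**3. Early withdrawals.** The assignment table in SAP 6.2.17.2 covers last diary days 1 to 80. Day 1 lands in Week 1 for 7 of the first 10 (Days 1 to 7) and for 4 in each of the ten later 7-day rows: 7 + 40 = 47 of 80. For the other 33 it is in no week. These are counts of possible days, not of subjects.

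**4. Size at Week 1.** Assume that the pre-dose night has an expected change of zero and that the other nights share a common expected change. With a Day 84 visit the Week 1 mean change is then 6/7 of its on-treatment value, a reduction of 1/7 = 14.3%.

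**5. A floor at Day 1 is not enough.** It would leave one pre-dose entry among 6, 5, 4 or 3 for visits on Days 83, 82, 81 and 80, which is 17% to 33%. The DSIS needs its floor at Day 2.

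**6. Baseline count.** Table 3 starts the DSIS after Visit 1. If Visit 1 is on Day -7, the first morning entry is on Day -6 and the window holds at most six entries (Days -6 to -1). The seventh pre-dose entry is the one on Day 1. If day-to-day errors are independent, the error variance of that baseline mean is larger by 7/6 = 1.17, about 17%. Subjects with a longer screening period can still supply seven pre-dose mornings.

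**7. The other end.** Table 3 footnote b ends diary completion on the night before the Week 12 visit. The DSIS Week 12 window includes the morning of that visit. If the footnote is followed, a Day 84 visit leaves Days 78 to 83, or six entries rather than seven.

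**The case against.** The strongest reply is that this is largely a choice of convention. Every entry in Days -7 to -1 is pre-dose, the window is pre-specified and identical in both randomised arms, and it averages whatever entries exist. Moving it by one day introduces no bias between arms. That stands, and it is why the point is minor.

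Several stronger readings are tempting, and the documents do not support them:

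- **That the Day 1 entry is always analysed as Week 1 data.** It is not. For visits on Day 85 or later it drops out altogether.
- **That a planned Week 1 treatment comparison is diluted.** SAP 6.11.2.1 plans the DSIS difference and p-value at Week 12 only; Week 1 gets LS means. The table list reuses the primary endpoint's shell, so a Week 1 difference might be printed, but it is not a stated comparison.
- **That every subject loses an entry.** Table 3 marks the DSIS at Visit 2 and Protocol 6.1 asks for it every morning, so a Day 1 entry is expected. Protocol 10.1, however, words the screening diary as covering the days before the Baseline Visit.
- **That the visit-day anchor at Week 12 shows a deliberate morning adjustment omitted at baseline.** The anchor table in SAP 6.2.18 also names rescue medication, which is recorded at bedtime, and footnote b points the other way.
- **That baseline precision falls by 17% throughout.** The figure needs Visit 1 on Day -7 and independent days. Subjects washing out a prohibited analgesic need at least two weeks, so they are not in that group, and its size is not given.

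It is also fair to say that most of the Week 1 problem for Days 80 to 83 comes from back-counting without a floor, which affects the NRS too: a Day 84 visit gives NRS Week 1 as Days -1 to 6. What is particular to the DSIS is the Day 1 morning.

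**Conclusion.** The mismatch is real and small. A Day 1 morning DSIS entry, where made before dosing, is always outside baseline. It is counted in Week 1 for completers seen on Days 80 to 84 and for some early withdrawals.

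The consequence is a reported DSIS Week 1 LS mean change pulled toward zero. For a subject seen on Day 84 this is about 14%; it is more for earlier visits if the rule is read literally, and nil from Day 85. The average over the trial depends on the spread of visit days, which the documents do not give.

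The Week 12 DSIS comparison is reached almost only through the baseline value. Week 1 sits in the same repeated-measures model and could matter slightly where Week 12 is missing. Nothing here shows bias between arms, and being first in the list of secondary endpoints adds no weight, because SAP Section 9 drops the hierarchical testing.

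The conclusion assumes that the Day 1 entry exists and was made on waking, before the clinic dose. Confidence is high on the window mismatch. Severity is minor.

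**What to change.** In SAP 6.2.2 and 6.2.18:

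- Define the DSIS baseline as the mean of the available morning entries from Day -6 to Day 1, using the Day 1 entry only if it was made before the first dose.
- Start DSIS Week 1 no earlier than Day 2. A Day 84 visit then gives Days 2 to 7 (six entries). A Day 80 visit gives Days 2 and 3 (two entries), so say whether so short a Week 1 is kept.
- Leave the NRS baseline at Days -7 to -1.

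Reconcile the visit-day anchor for DSIS Week 12 with Table 3 footnote b, so that it is clear whether a morning entry on the visit day is expected.

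The cost is two sentences and a one-day shift in the DSIS derivation, using diary data that the protocol already collects. The documents do not say whether the handheld device stores the time of entry. If it does not, the SAP should state that a waking entry on Day 1 is taken as pre-dose because the first dose is given in the clinic.

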6.2.3 Duration / Study Day / Time

Study day will be calculated as the number of days from first dose of study drug.

- date of event date of first dose of study drug + 1, for events on or after first dose
- date of event date of first dose of study drug, for events before first dose

6.2.4 Conventions for Missing and Partial Dates

All rules explained below for partial / missing dates will be followed unless contradicted by any other data recorded on the electronic Case Report Form (eCRF).

All dates presented in the individual subject listings will be as recorded on the eCRF (i.e., not completed as per the below rules).

6.2.5 Missing / Partial Start / Stop Date of Adverse Events (AE) and Concomitant Medications

Missing and partial start and stop date will be imputed for analysis purposes for Adverse Events (including Medical History) and Concomitant Medications as follows.

Partial or missing stop date will be imputed as follows:

- If the stop date is completely missing and the event has resolved, or the subject has stopped taking the concomitant medication, the stop date will be imputed as the date of the subject's last clinic visit in the study.
- If only the year is known, the stop date will be imputed as "31-Dec" of that year or as the date of the subject's last clinic visit in the study if in the same year.
- If the month and year are known, the stop date will be imputed as the last day of that month unless the stop date corresponds to the same month as the subject's last clinic visit in which case the date of subject's last clinic visit in the study will be used instead.

Missing start date will be imputed as follows:

- If the stop date occurs on or after the start of study drug or the event / concomitant medication is ongoing, the start date will be imputed as the date of the first dose of study drug.
- If the stop date occurs before the start of study drug, the start date of the event / concomitant medication will be imputed as the subject's screening date or the stop date of the event / concomitant medication whichever the earlier.

Partial start date (year present, but month and day missing)

- If the stop date occurs on or after the start of study drug or the event / concomitant medication is ongoing, and the year is the same as the year of first dosing the start date will be imputed as the date of the first dose of study drug. If the year is different from the year of first dosing "01-Jan" will be used.
- If the stop date occurs before the start of study drug, the start date of the event / concomitant medication will be imputed as the "01-Jan" of the same year.

Partial start date (month and year present, but day missing)

• If the stop date occurs on or after the start of study drug or the event / concomitant medication is ongoing, the start date will be imputed as the first day of the same month and

- year unless this partial start date is in same month as the first dose of study drug in which case the date of first dose of study drug will be used.
- If the stop date occurs before the start of study drug, the start date will be imputed as the first day of the month and year of the partial stop date.

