# 7. SELECTION AND WITHDRAWAL OF SUBJECTS

### 7.1. Subject Inclusion Criteria

#### **Inclusion Criteria: Screening**

Subjects must meet ALL the following criteria to be enrolled in this study:

- 1. An Institutional Review Board (IRB) approved written informed consent and privacy language (Health Insurance Portability and Accountability Act (HIPAA)) authorization must be obtained from the subject prior to performing any study -related procedures.
- 2. Consent to being included in a research subject database.
- 3. Subject is  $\geq 18$  and  $\leq 75$  years of age.
- 4. Diagnosis of Type 2 Diabetes.
- 5. At least moderate pain intensity over the last week as assessed by PGI-S at Visit 1.
- 6. Hemoglobin A1c (HbA1c)  $\leq 11\%$  (measured at Visit 1).
- 7. Stable use of diabetic medications beginning 1 month prior to Visit 1 (adequate glycemic control with diet and exercise alone is also permitted).
- 8. Diabetic peripheral neuropathy, of symmetrical nature and in lower extremities for ≥4 years (DPN in the upper extremities is not exclusionary).

- 9. Presence of pain due to diabetic neuropathy for at least 6 months prior to screening.
- 10. Total score of  $\geq$ 4 on the Michigan Neuropathy Screening Instrument.
- 11. Body mass index  $\leq 40 \text{ kg/m}^2$ .
- 12. Absence of impaired hepatic function. Impaired hepatic function is characterized by a previous known diagnosis of chronic liver disease, and/or abnormal serum total bilirubin (TBL), or alanine transaminase (ALT), aspartate transaminase (AST), or alkaline phosphatase (ALP)>1.5x upper limit of normal (ULN) at screening.
- 13. Calculated creatinine clearance  $\geq 60$  mL/minute (Cockcroft-Gault formula).
- 14. Fasting triglycerides  $\leq 600 \text{ mg/dL}$ .
- 15. Except as noted in criteria 12-14 above, clinical laboratory values must be within normal limits, or deemed not clinically significant by the Investigator.
- 16. Female subjects of child bearing potential with a negative pregnancy test prior to entry into the study and who are practicing a highly effective method of birth control (e.g., oral or parenteral contraceptives, intrauterine device, barrier [condom and spermicide], abstinence) and who do not plan to become pregnant, breastfeed, or donate ova during the course of the study and for 28 days after the final administration of investigational product.

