6.6 Baseline Comparability

Comparability of treatment groups with respect to subject demographics and baseline characteristics will be assessed in a descriptive manner.

Standard continuous or categorical variable summaries will be presented by treatment group and overall, for the following variables, for the Safety Population.

Demographic Data

- Age at Informed Consent (years)
- Sex (Male/Female)
- Ethnicity
- Race, where more than one race is selected the participant will be presented under the 'Multiple races' category in the summary but each selected race will be identified in the listing.

Baseline Characteristics

- Weight at Screening (kg)
- Height at Screening (cm)
- BMI at Screening (kg/m²)
- Childbearing Potential (for female subjects only)

Clinical Characteristics

- Discontinuation of prior analgesic medications at Baseline (Yes/No/NA)
- Duration of DPN at Baseline (years)
- Duration of Painful DPN at Baseline (years)
- Patient Global Impression of DPN Severity
- Neurological Examination at Baseline (Normal/Abnormal, Not Clinically Significant [NCS], Abnormal, Clinically Significant [CS])

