14.2.1.2.1	Exploratory Analysis (1): Average Pain Intensity Related to DPN, Change from Baseline to Week 12 in Weekly Mean NRS Score, By Baseline NRS Score, Mixed Model for Repeated Measures - Modified Intent-to-Treat Population	Stat IP	14.2.1.1.1
14.2.1.2.2	Exploratory Analysis (2): Average Pain Intensity Related to DPN, Change from Baseline to Week 12 in Weekly Mean NRS Score, Adjusted by Baseline BPI-DN Interference Composite Score, Mixed Model for Repeated Measures - Modified Intent-to-Treat Population	IP	14.2.1.1.1
14.2.1.2.3	Exploratory Analysis (3): Average Pain Intensity Related to DPN, Change from Baseline to Week 12 in Weekly Mean NRS Score, Adjusted by Baseline DSIS Score, Mixed Model for Repeated Measures - Modified Intent-to-Treat Population	IP	14.2.1.1.1
14.2.1.2.4	Exploratory Analysis (4): Average Pain Intensity Related to DPN, Change from Baseline to Week 12 in Weekly Mean NRS Score, Adjusted by Duration of DPN at Baseline, Mixed Model for Repeated Measures - Modified Intent-to-Treat Population	IP	14.2.1.1.1
14.2.1.2.5	Exploratory Analysis (5): Average Pain Intensity Related to DPN, Change from Baseline to Week 12 in Weekly Mean NRS Score, Adjusted by Duration of Painful DPN at Baseline, Mixed Model for Repeated Measures - Modified Intent-to-Treat Population	IP	14.2.1.1.1
14.2.1.3.1	Subgroup Analysis (1): Average Pain Intensity Related to DPN, Change from Baseline to Week 12 in Weekly Mean NRS Score, By Baseline NRS score, Mixed Model for Repeated Measures - Modified Intent-to-Treat Population	IP	14.2.1.1.1
14.2.1.3.2	Subgroup Analysis (2): Average Pain Intensity Related to DPN, Change from Baseline to Week 12 in Weekly Mean NRS Score, By Prior Analgesic Use, Mixed Model for Repeated Measures - Modified Intent-to-Treat Population	IP	14.2.1.1.1

14.2.1.3.3	Subgroup Analysis (3): Average Pain Intensity Related to DPN, Change from Baseline to Week 12 in Weekly Mean NRS Score, By Subjects Sourced Via AES, Mixed Model for Repeated Measures - Modified Intent-to-Treat Population	IP	14.2.1.1.1
14.2.1.3.4	Subgroup Analysis (4): Average Pain Intensity Related to DPN, Change from Baseline to Week 12 in Weekly Mean NRS Score, By Subjects Sourced Via AES and Baseline NRS Score, Mixed Model for Repeated Measures - Modified Intent-to-Treat Population	IP	14.2.1.1.1
14.2.2	Secondary Efficacy Endpoints	IP	

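### SAP 6.2.5 applies the adverse-event date rules to Medical History, so some conditions that ended before screening, or whose onset is unknown, are dated to the last clinic visit or the first dose

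*SAP*

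**What the plan says.** SAP 6.2.5 sets one rule set for three kinds of record: "Missing and partial start and stop date will be imputed for analysis purposes for Adverse Events (including Medical History) and Concomitant Medications as follows". The rules that matter here are these:

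- **Stop missing, condition resolved:** "the stop date will be imputed as the date of the subject's last clinic visit in the study". A year-only or month-and-year stop also becomes the last clinic visit when it falls in the same year or month as that visit. Otherwise it becomes 31 December or the month end.
- **Onset wholly missing:** where the "event / concomitant medication is ongoing, the start date will be imputed as the date of the first dose of study drug". The same applies when the stop, recorded or imputed, is on or after first dose. If the stop is before first dose, onset is the earlier of screening and the stop date.
- **Onset partial, condition ongoing or stop on or after first dose:** first dose if the recorded year (or month and year) is that of first dose. Otherwise 1 January, or the first of the recorded month.
- **Onset month and year known, stop before first dose:** "the start date will be imputed as the first day of the month and year of the partial stop date".

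SAP 6.2.4 suspends any rule that other eCRF data contradict, and keeps recorded dates in the listings.

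Protocol 9.4.2 describes a pre-existing condition as one present before dosing and reported as medical history. SAP 6.7 tabulates prior and ongoing conditions at Screening separately (Tables 14.1.3.1 and 14.1.3.2). SAP 6.6 lists duration of DPN and of painful DPN at baseline, in years, with no formula. SAP 11 lists two exploratory primary-endpoint models that use them: Table 14.2.1.2.4 (DPN duration) and Table 14.2.1.2.5 ("Adjusted by Duration of Painful DPN at Baseline"). Inclusion criterion 8 requires DPN for at least 4 years. Criterion 9 requires "Presence of pain due to diabetic neuropathy for at least 6 months prior to screening".

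**The concern.** For an adverse event of uncertain date, assuming onset at first dose is the cautious choice, because the event then counts as treatment-emergent. Medical history has no such worst case. It is collected at Visit 1 and lies before dosing, so an imputed date at or after first dose is wrong for it.

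Two outputs are at stake. The first is the split between prior and ongoing history, if it is programmed from imputed dates. The second, on a condition the documents leave open, is DPN and painful-DPN duration. Protocol 6.2 names long-standing disease (at least 4 years) as part of the reason for choosing this population, so the duration summaries and the two duration-adjusted models should rest on a defined variable.

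**Working it through.** The plan gives no figure to reproduce here; the check is to apply the rules as written. Dates assumed for illustration:

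- screening 15 Feb 2021
- first dose 15 Mar 2021 (28 days after screening)
- last clinic visit 6 Jun 2021 (Day 84)

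Duration = (first dose − imputed onset in days) / 365.25.

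| History record | Imputed onset | Imputed stop | Years before first dose |
|---|---|---|---|
| Ongoing, onset missing | 15 Mar 2021 | – | 0.000 |
| Resolved, both dates missing | 15 Mar 2021 | 6 Jun 2021 | 0.000 |
| Stop 2021, onset missing | 15 Mar 2021 | 6 Jun 2021 | 0.000 |
| Resolved, stop missing, onset 2010 | 1 Jan 2010 | 6 Jun 2021 | 11.20 |
| Ongoing, onset 2021 | 15 Mar 2021 | – | 0.000 |
| Ongoing, onset Mar 2021 | 15 Mar 2021 | – | 0.000 |
| Ongoing, onset 2015 | 1 Jan 2015 | – | 6.20 |
| Ongoing, onset Jun 2015 | 1 Jun 2015 | – | 5.79 |
| Stop 2018, onset missing | 31 Dec 2018 | 31 Dec 2018 | 2.20 |
| Stop 2018, onset Jun 2010 | 1 Dec 2018 | 31 Dec 2018 | 2.29 |

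**Stop dates.** Rows 2 to 4 cover conditions that may have ended before screening. Each is given a stop after first dose, so date-based programming would count it as ongoing at screening. In rows 2 and 3 the whole condition falls inside the treatment period. The rules act in sequence: the imputed stop is after dosing, which then sends the missing onset to first dose.

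**Onset dates.** Row 1 gives 0.000 years. With one day added it is 1 / 365.25 = 0.003; measured at screening it is −28 / 365.25 = −0.077. None of these is compatible with at least 4 years of DPN or at least 6 months of pain.

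**Which zeros can arise for DPN.** A wholly missing onset can produce a zero for either duration. A year-only onset in the first-dose year cannot arise for DPN in an eligible subject, since it would fail criterion 8. It can arise for painful DPN only when screening falls at least 6 months into that year. A month-and-year onset in the month of first dose would fail both criteria, so for an eligible subject it concerns other history conditions only.

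**Dates that do not move to dosing.** Rows 7 to 10 stay before dosing. Row 10 shows a separate slip: the recorded onset of June 2010 is discarded in favour of the stop month. The parallel bullet for ongoing items uses the onset's own month and year, so this looks like a drafting error. It affects only items that ended before dosing and changes no planned classification.

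**The case against.** The strongest reply is the override in SAP 6.2.4. History is recorded at Visit 1, and eligibility is checked and listed (Listings 16.2.4.3 and 16.2.4.4). A DPN onset on the day of first dose contradicts those records, so the rule would lapse. This largely answers a literal zero, but the clause gives no substitute value. The result may be a missing duration, but the SAP does not say so.

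The source of the durations is also unstated. They appear under Clinical Characteristics in SAP 6.6, apart from Medical History in 6.7, and SAP 6.2 says variables derived in the source data will not be re-calculated. Section 6.11.1.5, to which 6.11.2.1 refers, is not in the visible text and might hold a definition. This objection stands: the duration consequence is conditional.

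For the tables, the stop rule in 6.2.5 itself relies on knowing whether a condition has resolved, and a programmer could use that status directly. Nothing in the SAP requires this, so the ambiguity remains.

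Two stronger readings are tempting. A reader might infer that every incomplete history date is moved to dosing; rows 7 to 10 show otherwise. A reader might also infer that the duration-adjusted treatment differences would be biased. The documents do not support that: duration is a pre-randomisation covariate, and error in it costs some precision without biasing a randomised comparison.

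**Conclusion.** The point holds as a minor defect. SAP 6.2.5 explicitly brings Medical History under rules that can place a resolved condition's stop at the last clinic visit and an unknown onset at first dose, against Protocol 9.4.2. The firmer consequence is that resolved conditions may be shown as ongoing in Tables 14.1.3.1 and 14.1.3.2; this assumes the split is made from imputed dates. The weaker one is a duration of about 0 years in the baseline table and in Tables 14.2.1.2.4 and 14.2.1.2.5. That needs the durations to come from imputed history dates and the override not to be applied.

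The primary and secondary analyses use none of these dates, and the listings show dates as recorded. The frequency of incomplete history dates is not given, so the size of the effect cannot be determined.

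**What to change.** 1. Remove Medical History from SAP 6.2.5.
2. Classify prior versus ongoing history from the eCRF status. If a stop must be imputed for a resolved condition, set it no later than the day before screening.
3. State in SAP 6.6 that DPN and painful-DPN duration are derived from the recorded onset, and are left missing when the onset year is unknown. Onset is never imputed to first dose.
4. As an accompanying correction, make the last bullet of 6.2.5 use the month and year of the partial start date, not of the stop date.

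The cost is a short SAP paragraph and a small programming change, best settled before unblinding. The downside is that a few durations may become missing, and those subjects would drop out of the two exploratory models that use duration unless the SAP says how to handle them.
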